### 1. Abstract

#### Introduction:

Resin-based composites (RBCs) have become the gold standard in restorative dentistry due to their superior aesthetics, adhesion, and minimally invasive application. However, wear remains a critical drawback, compromising their longevity and clinical performance. Various techniques have been suggested to measure the clinical performance of (RBCs). Recent advancements in digital dentistry, such as intraoral scanning, offer a more precise and efficient approach for quantitative wear assessment.

#### Aim:

This study aims to evaluate wear resistance and bioactivity of self cured bioactive resin composite vs nanhybrid resin composite.

#### Methodology:

Twelve healthy patients with 24 carious molar teeth will be selected where each patient should have two ocluso- mesial cavities. Standardized

occluso- mesial cavities will be prepared for all the selected teeth, for each patient the first tooth will be restored with conventional nanohybrid RBC (M1). Meanwhile, the second tooth will be restored by self-cure bioactive RBC (M2). Then, wear resistance will be evaluated by intraoral scanner immediately after restoration (T0), six months later (T1), after 12 months (T2), 18 months (T3) and 24 months (T4). Software analysis will be done by superimposing the 3D digital impression and evaluate the restoration wear by calculating the 3D volume loss.

Also, bioactivity of the restoration will be measured by measuring the mineral density beneath the restoration. Digital radiographic images will be taken for the restoration by parallel technique and grey scale of the pixels under restoration will be measured by software immediately after restoration (D0), one month later (D1) and after 3 months (D2).

## **2. Introduction and Background**

Resin-based composites (RBCs) are currently the most widely used materials for dental restorations due to their favorable esthetics, mechanical properties, cost-effectiveness, versatility, and overall acceptable clinical performance. However, their long-term clinical durability remains a concern and requires further enhancement (**Ferracane, 2024**).

Among the major causes of failure and replacement of resin composite restorations is secondary caries, with incidence rates reaching approximately 60%. This high rate highlights a significant

limitation in the longevity of conventional resin based restorative materials (**Pinto et al., 2023**).

In last few decades, bioactive resin composite materials have emerged as a trial to overcome such a problem. These materials are designed to release ions, such as calcium and phosphate, in a controlled and localized manner at the tooth-restoration interface. This ion exchange with surrounding saliva and tooth structure contributes to maintaining mineral balance and promoting remineralization, thus supporting tooth integrity and preventing its demineralization (**Garcia et al., 2021**).

Recently, self cured resin based bioactive bulk fill material (**Stela, SDI, Australia**) was launched to the market as a recent bioactive RBC that contains fluoride, calcium and strontium for enhanced biomimetic and bioactive properties. Unfortunately, bioactive RBCs, vary significantly in formulation, particularly in terms of the type, size, and concentration of ion-releasing components. These differences influence their solubility, permeability, and ultimately their ability to sustain ion release over time. While such modifications are beneficial for caries prevention, they may also compromise the physical properties of such materials, especially wear resistance under continuous masticatory forces. This becomes even more critical considering that wear behavior of dental RBCs is highly dependent on their chemical constituents (**Garcia et al., 2021**).

It is worth mentioning that occlusal wear is a critical factor affecting the success of posterior composite restorations. So that, high wear resistance is essential for maintaining the function and longevity

of restorations. In contrast, poor wear resistance can lead to clinical complications such as tooth shifting, temporomandibular joint discomfort, and periodontal issues (**Garcia et al., 2021**).

The manufacturer claimed that **Stela** is an innovative bioactive material with high strength properties. It offers an unlimited depth of cure and low-stress polymerization with a gap-free interface (**SDI Limited, 2023**). Therefore, the primary objectives of this study are to clinically evaluate the wear resistance and the bioactivity of such material.

Wear behavior of a micro hybrid composite vs. a nanocomposite in the treatment of severe tooth wear patients was evaluated. A convenience sample of 16 patients with severe tooth wear was chosen. Eight of them were treated with a micro hybrid composite (Clearfil APX, Kuraray) and the other eight with a nanocomposite (Filtek Supreme XTE, 3M). The Direct Shaping by Occlusion (DSO) technique was used for all patients. Clinical records were collected after 1 month (baseline) as well as 1-, 3- and 5-years post-treatment. The maximum height loss at specific areas per tooth was measured with Geomagic Qualify software. The results showed that for premolar and molar teeth, Filtek Supreme showed less wear in bearing cusps, whereas Clearfil APX showed less wear in non-bearing cusps. They concluded that nanocomposite restorations showed significantly less wear at bearing cusps, whereas microhybrid composite restorations showed less wear at non-bearing cusps and anterior maxillary teeth (**Ning et al, 2021**).

Remineralization effect of natural versus synthetic materials on

deep carious dentin was studied. Extracted human molars with class I carious lesions were collected and randomly assigned into four groups: a control group, a propolis-treated group, a hesperidin-treated group, and a group treated with silver diamine fluoride (SDF). Carious tissues were managed using the stepwise caries removal approach, followed by application of the respective test materials. All cavities were then restored using glass ionomer cement (GIC). Radiographic evaluations were conducted at 6 and 12 weeks to assess changes in mineral density. Among the tested groups, the propolis group exhibited the greatest increase in mineral density, while the hesperidin group recorded the lowest with no significant difference. The findings suggested that both propolis and hesperidin demonstrated notable potential in enhancing dentin remineralization and limiting caries progression, presenting viable alternatives to SDF (*Anani et al. 2023*).

Clinical performance and wear resistance of milled resin composite material versus direct nanohybrid bulk-fill resin composite in the restoration of endodontically treated posterior teeth over 1 year was studied. Twenty-six patients with endodontically treated teeth were divided into two groups, where R1 restored with Milled composite, R2 restored with direct bulk-fill composite. Each restoration was assessed for wear resistance immediately and after one year intraorally and extraorally using intraoral scanners and three-dimensional surface-based superimposition software. They found that direct nanohybrid bulk-fill resin composite showed a greater amount of wear without a statistically significant difference. There was no significant reliability/agreement between both methods. They concluded that both milled composite and

direct bulk-fill resin composite restorations in endodontically treated teeth demonstrated minimal wear over a 1-year follow-up period (*Elhaddad et al., 2024*).

An evaluation of dental paste-like bulk-fill composite wear using intra-oral scanner was done. Six different dental composite materials, including five bulk-fill composites and one conventional composite, were tested alongside natural human enamel as a control group. A computer-controlled chewing simulator was used for wear testing. A one-way ANOVA test was used to identify any significant differences between the means of the tested dental composite materials. The results showed variability among bulk-fill composites, with some demonstrating wear resistance like conventional composites. Significant variability was observed among bulk-fill composites, but the results were comparable to those of conventional composites. The enamel control group demonstrated the lowest wear values, with some bulk-fill composites showing similar wear resistance. The conclusion showed that significant variability was observed among bulk fill composites, but the results were comparable to those of conventional composites. The enamel control group demonstrated the lowest wear values, with some bulk-fill composites showing similar wear resistance (*Baltacioglu et al., 2024*).

The wear of dental restorations using an intraoral scanner and its correlation with visual assessment was evaluated prospectively. Thirty six patients were followed-up by intraoral optical impression and visual assessment over three appointments over 12 months, where T0 is the base line, T6 after 6 months, and T12 after 12 months. The results

showed that: According to the visual indices, all restorations in this study were clinically healthy. However, in the digital measurement of wear, 94.74% and 94.44% of the restorations during the T0-T6 and T6-T12 observation periods, respectively, showed deterioration greater than 41 microns. Discordant results were obtained in the correlation analysis. In T0-T6, the results were not considered statistically significant; however, the results obtained during T6-T12 showed a correlation. They concluded that wear of dental materials as observed by the human eye did not agree with that observed by intraoral scanning. The scanner effectively measures wear, detecting details that are beyond the capability of the human eye and conventional photographs (*Urcelay et al, 2025*).

Digital and conventional methods of wear analysis using two hybrid ceramic materials were compared. Disc-shaped samples (2 mm thick and 10 mm in diameter) were prepared from Vita Enamic and Cerasmart materials and subjected to chewing simulation. Wear evaluation was conducted using two approaches: conventional weight loss assessment before and after simulation, and digital analysis via Geomagic software by superimposing 3D scan images taken with intraoral scanner. The results revealed a positive correlation between the conventional and digital measurement methods. Statistically significant differences were observed between the two materials in terms of wear behavior. Vita Enamic demonstrated considerably more wear than Cerasmart 270 across both evaluation techniques. They concluded that both weight-based and digitally calculated volume loss methods are reliable for wear assessment, with Cerasmart 270 showing

superior resistance to wear compared to Vita Enamic (ElSharouny et al, 2025).

### **3. Research Q (RQ):**

What is the difference between self cured bioactive and light cured nanohybrid (RBCs) regarding wear resistance and bioactivity after two years of clinical performance?

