#### **c. Objectives**

- 1- Assessment of wear resistance of self cured bioactive RBC in comparison to light cured nanohybrid one.
- 2- Evaluation of bioactivity of self cured bioactive RBC in comparison to light cured nanohybrid one.

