#### **II-7- Assessment of the bioactivity:**

Bioactivity of each examined restoration will be determined by the evaluation of mineral density beneath the tested materials. Immediately after restoration (D0), an image plate digital sensor (Xios XG Supreme, Dentsply Sirona, UK) will be used for transmitting the radiographic

image of the selected tooth to the computer. A posterior parallel kit will be used for image standardization. Later, each restoration will be examined at standardized follow-up periods; one month (D1) and three months (D2) (Table 4 and 5). The image plate will be inserted at one end of the parallel kit, while the other end was connected to the x-ray cone. All the radiographs will be evaluated for the outcome by a software (ImageJ software, NIH, USA). The assessment of mineral density will be done by the software through performing the following measurements: in each image a line will be drawn along the CEJ to act as a reference, while another parallel line will be drawn at the bottom of the cavity. The distance between both lines will be standardized for each tooth by measuring the length of a vertical line connecting them. The length of the line centralized at the bottom of the cavity will be determined in pixels directly via the previously mentioned software. Such length will be fixed for each sample throughout assessment intervals. Three points on this line (at its start, middle and end) will be determined. The mineral density value at each of these points will be identified by taking the corresponding three readings from the software and recording them to calculate the average value. The mineral density mean value will be calculated from the software (Ibrahim et al, 2016).

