**Table 4: Variables of the bioactivity test and levels of investigations:**

Variable	Level	Referred to
Type of material (M).	M1	Light cured nanohybrid RBC.
	M2	Self-cured bioactive RBC.
Time of follow-up for mineral density (D).	D0	Immediately after restoration.
	D1	After one month.
	D2	After three months.

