**Table 5: Interaction between variables for bioactivity test:**

M		Type of material (M)		Total
		M1	M2	
Times (D)	D0	M1D0	M2D0	
	D1	M1D1	M2D1	
	D2	M1D2	M2D2	
Total		10	10	20

Sample size: n= 10

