### **8. Time Plan**

**Starting** after approval of the ethical committee and faculty council.

**Ending** after 24 months.

Activity/Month	-	2	3	4	5	6	7	8	9	10	11	12	13	14	15	16	17	18	19	20	21	22	23	24
Patient selection																								
Material application																								
Statistics																								
Writing																								
Revision																								

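### The research question asks about bioactivity at two years, but its only measure, mineral density, stops at three months; the 24-month time plan also ends before the 24-month wear scan

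*Protocol*

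**What the plan says.** **Research question.** Section 3 of the Protocol asks for the difference between the self-cured bioactive composite and the light-cured nanohybrid composite "regarding wear resistance and bioactivity after two years of clinical performance". One time horizon covers both outcomes.

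**What bioactivity means.** Section II-7 states: "Bioactivity of each examined restoration will be determined by the evaluation of mineral density beneath the tested materials". The Protocol names no other bioactivity measure.

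**When it is measured.** The Methodology part of the abstract, Section II-7 and Table 4 agree on three readings: immediately after restoration (D0), at one month (D1) and at three months (D2). Table 4 describes the last level as "After three months". Table 5 carries the codes D0 to D2 and nothing later.

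**When wear is measured.** The abstract, Section II-6 and Table 2 give T0 (immediately after restoration) and 6, 12, 18 and 24 months (T1 to T4).

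**Status of the bioactivity outcome.** Section 4c lists it as the second of two objectives: "Evaluation of bioactivity of self cured bioactive RBC in comparison to light cured nanohybrid one". Section 2 describes wear and bioactivity together as the study's primary objectives. The hypothesis, aim and objectives in Section 4 give no time horizon for either.

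**Time plan.** Section 8 sets the start with "Starting after approval of the ethical committee and faculty council" and the end at 24 months. Its chart has 24 monthly columns, and patient selection and material application are among its activities.

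**The concern.** The research question sets the horizon at which the conclusion will be read. Here it is the only place that attaches a horizon to the bioactivity objective, and the horizon it attaches is one at which bioactivity is never observed. The expected outcomes in Section 4d forecast a marked bioactive effect, also without a time limit. A reader could therefore take a grey-scale comparison at three months as evidence about the material at two years.

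The time plan raises a separate and smaller question. If the study ends 24 months after it starts, and patients must be selected and treated within that time, a scan due 24 months after restoration falls outside the plan. A final analysis run at the stated end would then lack the two-year wear data on which the other half of the research question depends.

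**Working it through.** **1. Bioactivity horizon**

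| Item | Value | Source (Protocol) |
|---|---|---|
| Horizon asked for | 2 years = 24 months | Section 3 |
| Only measure of bioactivity | Mineral density beneath the restoration | Section II-7 |
| Last reading (D2) | 3 months | Abstract (Methodology), Section II-7, Table 4 |

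- Share of the horizon observed: 3 / 24 = 0.125, or 12.5%.
- Months with no reading: 24 − 3 = 21.

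The three places that state the density schedule in months agree with one another, and the codes in Table 5 fit them. The sentence in Section 3 is the outlier. Nothing in Section 4 corrects it, because the hypothesis, aim and objectives name no time point.

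**2. Time plan**

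Inputs: the stated end is month 24 (Section 8), and T4 is 24 months after restoration (abstract, Section II-6, Table 2). Let *s* be the months from study start to placement of a given restoration.

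- T4 falls at study month *s* + 24.
- Overrun past the stated end = (*s* + 24) − 24 = *s*.

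The overrun is zero only if *s* = 0, that is, if the tooth is restored at the moment the study starts. Placement one month in puts T4 at month 25. Patients have to be selected before they are treated, so *s* = 0 for every patient is not realistic. No total overrun is given, because the tick positions in the Section 8 chart are uncertain in the text available and the Protocol gives no other value for *s*.

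**The case against.** The strongest reply is that this is one loosely worded sentence. Every passage that governs conduct gives the density schedule clearly and consistently, and no visit, image, test or sample size depends on the research question. The reference to two years may have been meant for wear alone, or for the length of the study as a whole. Misreporting is only a possibility, since the last density reading is labelled as three months wherever its timing is stated.

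Much of this is fair, and it bears on how serious the point is. It does not remove the contradiction. The sentence joins both outcomes under one horizon, and no other passage limits it to wear.

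A second reply is that the documents do not show which side reflects the intent: the question could be narrowed, or a 24-month density reading could be added. That stands. Both would reconcile the text. The agreement of the schedule statements makes narrowing the question the natural repair, and it is the one that changes no procedure.

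On the time plan, Section 8 does not say from when the 24 months run, and an administrative chart does not cancel a visit that the methods fix relative to restoration. Both points stand, so follow-up to T4 is not in doubt. But the start is given immediately before the end, and the chart places selection and placement within its 24 columns. Even if 24 months of follow-up was meant, the chart does not show it.

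**Conclusion.** The concern holds. The bioactivity half of the research question cannot be answered at the horizon it names: readings cover 3 of 24 months (12.5%) and the last 21 months have none. This rests on the Protocol's own text and needs no outside figure.

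The time-plan mismatch also holds, as a secondary and administrative point. It assumes that the 24 months in Section 8 run from study start, as the chart implies. On that reading, the stated end precedes T4 by the time from study start to placement, for every tooth not restored on the first day.

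Neither point affects the validity of the wear comparison or the three-month density comparison. Both are wording errors that should be corrected, because one concerns the horizon of a stated primary objective and the other the date by which the two-year wear data can exist.

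**What to change.** - **Section 3:** restate the question as wear resistance over two years and bioactivity, measured as mineral density, over three months. State that the bioactivity conclusion is limited to three months.
- **Section 8:** define the study end as the date of the last restoration plus 24 months, place the final statistics after the last T4 visit, and redraw the chart to match.

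If the sponsor did intend a two-year bioactivity result, the density schedule would have to change instead. That would add imaging and is a decision for the sponsor.

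The cost of the recommended change is wording in two sections. The stated end date moves by the time from study start to the last placement, which the planned 24-month follow-up already implies. No visits, images or patients are added, and the wear and density schedules stay as they are.

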### **4. Research Hypothesis, Aim, Objectives & Expected Outcomes**

#### **a. Hypothesis**

Null hypothesis: There is no significant difference between wear resistance and bioactivity between self cured bioactive RBC and light cured nano-hybrid one.

#### **b. Aim**

This study aims to evaluate wear resistance and bioactivity of self cured bioactive RBC in comparison to light cured nanohybrid one.

#### **c. Objectives**

- 1- Assessment of wear resistance of self cured bioactive RBC in comparison to light cured nanohybrid one.
- 2- Evaluation of bioactivity of self cured bioactive RBC in comparison to light cured nanohybrid one.

#### **d. Expected Outcomes**

Self cured bioactive RBC could show slight lower wear resistance than light cured nano-hybrid RBC with remarkable bioactive potential.

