## 6- Sample size calculation:

Sample size calculation was performed using G\*Power version 3.1.9.2, (Faul *et al*, 2007) University Kiel, Germany. Copyright (c) 1992-2014.

$$f = \frac{\sigma_\mu}{\sigma}$$

[figure not shown]
$$\sigma_\mu^2 = \frac{\sum_{i=1}^k n_j (\mu_i - \mu)^2}{N}$$

Where:

$f$ : is the effect size;  $\alpha = 0.05$ ;  $\beta = 0.05$ ; Power =  $1 - \beta = 0.80$

The effect size  $d$  was **1.22 (large)** according to the previous studies (**Elderiny et al., 2024**) with alpha ( $\alpha$ ) level of 0.05 and Beta ( $\beta$ ) level of 0.05, i.e., power = 80%; the estimated sample size ( $n$ ) should be **20** samples and will be divided into **two groups**.

To account for dropouts, the sample size will be expanded by 20%, which produced 12 restorations for each group instead of 10.

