### Statistical analysis:

All collected data will be calculated, tabulated, and statistically analyzed using suitable statistical tests as follows: **A normality test:** will be done to check normal distribution for data by Shapiro-Wilk test. **Descriptive statistics:** will be calculated in the form of mean  $\pm$  standard deviation (SD), range (Max-Min). Qualitative data will be presenting as (%) frequencies (n) and percentages. **T- test or Mann-Whitney test**

**(According to the types of data).** Independent Student's T-test or Mann-Whitney will be performed for pair wise comparison between groups in each time at P value < 0.05. **The Chi-square test** will be used to test significance of association between categorical variables. **Pearson's correlation coefficient:** will be used for estimating the relationship between quantitative variables. **P<0.05** is considered significant. Statistical analysis will be performed using the computer program SPSS software for windows version 26.0 (statistical package for social science, ARMONK, NY: IBM Corp).

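### If the slight wear deficit the protocol expects is a small-to-moderate effect, 10 to 12 pairs would seldom detect it, and the planned independent test is weaker still than a within-patient estimate

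*Protocol*

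**What the plan says.** Four places in the protocol bear on this.

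- **Section 4.d, Expected Outcomes:** "Self cured bioactive RBC could show slight lower wear resistance than light cured nano-hybrid RBC with remarkable bioactive potential". No size is given, in mm³ or in SD units.
- **Section 3, Research Q:** the question is one of size, "What is the difference between self cured bioactive and light cured nanohybrid (RBCs) regarding wear resistance", and continues to bioactivity.
- **Section 6, Sample size calculation:** the effect size d is "1.22 (large) according to the previous studies". The outcome it belongs to is not named. The total "should be 20 samples and will be divided into two groups", and then: "To account for dropouts, the sample size will be expanded by 20%, which produced 12 restorations for each group instead of 10".
- **Statistical analysis:** means, SDs and ranges are to be tabulated. An independent t-test or Mann-Whitney test "will be performed for pair wise comparison between groups in each time at P value < 0.05". This is the only between-material comparison specified for a continuous outcome.

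The Abstract and section II-4 make the design within-patient: twelve patients with two molars each, one per material, with the allocation of material to molar randomised.

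**The concern.** Wear is the first listed objective. The Introduction explains why: ion-releasing formulations may give up physical properties, wear resistance above all. A modest wear penalty is therefore the result that the trial most needs to measure well.

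The stated 80% power belongs to an effect the protocol itself calls large, whereas the wear effect it anticipates is called slight, and nothing connects the two. The planned comparison also treats the two restorations in one mouth as unrelated, which discards the precision that the within-patient design provides. If the true deficit is modest, the likely result is P≥0.05 at each visit, with no interval to show how large a deficit remains possible.

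**Working it through.** **1. The plan's own figure.** The inputs from section 6 are d = 1.22, α = 0.05, power 80% and 10 per group. Sidedness is not stated.

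- Normal approximation, two-sided: n per group = 2(1.960 + 0.842)²/1.22² = 10.5, rounded up to 11 (22 in total).
- Noncentral t, one-sided: 10 per group, power 83.6%.
- Noncentral t, two-sided: power is 73.2% at 10 per group and 81.5% at 12.

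So 20 is reproduced exactly by a one-sided t-test and to within two restorations by the two-sided normal formula. Section 6 also gives β as 0.05 beside 80% power; read literally, that would need 18 to 19 per group. This is a separate slip and does not affect what follows.

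**2. Power for a smaller effect.** Assumptions: slight means d = 0.2 to 0.5; the within-patient correlation r is 0.5; the test is two-sided at 0.05.

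- Paired t: dz = d/√(2(1 − r)), noncentrality dz√n, n − 1 df. At r = 0.5, dz = d.
- Independent t applied to paired data: simulated, 40,000 trials per cell, bivariate normal, r = 0.5.

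| d | Paired, 10 pairs | Paired, 12 pairs | Independent, 10 per group | Independent, 12 per group |
|---|---|---|---|---|
| 0.2 | 8.8% | 9.7% | 2.2% | 2.4% |
| 0.3 | 13.6% | 15.8% | 4.1% | 4.9% |
| 0.5 | 29.3% | 35.3% | 12.0% | 14.9% |

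The independent test falls below the usual unpaired power (7%, 10% and 18.5% at 10 per group, which assume r = 0). Positive correlation shrinks the true variance of the difference, but the test's standard error does not shrink with it.

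**3. Sensitivity to the correlation (paired test, 10 / 12 pairs).**

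| d | r = 0.3 | r = 0.7 | r = 0.8 |
|---|---|---|---|
| 0.2 | 7.7% / 8.4% | 11.3% / 13.0% | 14.6% / 17.1% |
| 0.3 | 11.1% / 12.7% | 19.5% / 23.2% | 26.9% / 32.3% |
| 0.5 | 22.3% / 26.7% | 44.6% / 53.2% | 60.6% / 70.4% |

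Power passes 50% only at d = 0.5 with high correlation. The paired test reaches 80% power at dz = 1.00 (10 pairs) or 0.89 (12 pairs), which at r = 0.5 are also the values of d.

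**4. What a non-significant result leaves open.** The half-width of the 95% CI for the mean within-patient difference, in SD units, is t(0.975, n − 1) × √(2(1 − r)/n).

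- 10 pairs: 2.262 × √(0.6/10) = 0.55 at r = 0.7; 2.262 × √(1.4/10) = 0.85 at r = 0.3.
- 12 pairs: 2.201 × √(0.6/12) = 0.49 at r = 0.7; 2.201 × √(1.4/12) = 0.75 at r = 0.3.
- An interval built as for independent groups: 2.101 × √(2/10) = 0.94 with 10 per group; 2.074 × √(2/12) = 0.85 with 12.

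These half-widths are the confidence limits only if the observed difference is exactly zero. An estimate just short of significance has its far limit close to twice the half-width.

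**The case against.** The strongest objection is that slight and large may sit on different scales. Slight is an unquantified and hedged expectation, while large labels a standardised d. If the SD of wear between teeth is small, a slight difference in mm³ could be a large d. Section 6 also never says that 1.22 is a wear effect, and the Expected Outcomes section anticipates a remarkable effect on bioactivity. This stands. A reader might infer that the protocol contradicts itself by sizing wear on an effect that it does not expect, but the text does not go that far. It shows that the two statements are not connected and that no figure is given to connect them.

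A reader might also infer that P≥0.05 will be reported as no difference in wear. No passage says so. The null hypothesis is loosely worded but conventional, no equivalence or comparability conclusion is planned, and the summary of another trial in the Introduction does not show how this one will report. Nor does the protocol rely on P values for all its reporting: group means and SDs will be given, and a crude difference can be read from them.

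Finally, a confidence interval is often left to the SAP. Its absence alone would not be a finding. The choice of an independent comparison for within-patient data is different, because the protocol itself fixes that method and a better one is available from the same measurements.

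**Conclusion.** The point holds as a conditional one. If slight means d = 0.2 to 0.5 and the within-patient correlation is 0.5, a real wear deficit would be detected with about 9% to 35% power by a paired test and about 2% to 15% by the planned independent test. A non-significant wear result would be likely, and even an observed difference of zero would leave deficits of about 0.5 to 0.85 SD unexcluded in a paired analysis.

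The d range and the correlations are assumptions, since the protocol states neither. At d = 0.5 with a correlation of 0.7 to 0.8, a paired test has 45% to 70% power, so the shortfall is not uniform. At d = 0.2 to 0.3 it stays at or below 32% even at a correlation of 0.8. Whatever the true effect, the 80% figure supports only d = 1.22, and with positive within-patient correlation the independent test wastes precision. The documents do not show that the trial intends to claim equal wear.

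**What to change.** **Statistical analysis section.** Replace the independent comparison with the mean within-patient difference (M2 minus M1) and its 95% CI for each outcome, from a paired analysis. State that P≥0.05 will not be interpreted as evidence of equal wear.

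**Section 6.** Name the outcome behind d = 1.22. State that the 80% power applies to that effect only and not to a slight wear difference. If a wear difference and SD in mm³ are available, give them, so that a reader can see what slight means in SD units.

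A formal equivalence margin is optional, because the trial claims no equivalence. With intervals this wide, only a generous margin could be met.

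**Cost.** Changes to wording and one additional output from data already being collected, with no more patients, visits or measurements. The downside is that a non-significant wear result can no longer be presented as comparability. The change improves precision and reporting, but it does not make the trial adequately powered for a small deficit.
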